## 5 Population

Approximately 108 subjects with biopsy-proven lichen planus will be randomized in the study and assigned to 3 cohorts according to their predominant lichen planus subtype (predominantly cutaneous lichen planus, predominantly mucosal lichen planus or lichen planopilaris).

Each cohort will enroll 36 patients randomized in a 2:1 ratio (24 patients will enter the active arm, 12 patients the placebo arm).

Drop-outs after randomization will not be replaced.

### 5.1 Inclusion criteria

Subjects eligible for inclusion in this study must meet **all** of the following criteria:

1. Written informed consent must be obtained before any assessment is performed.
2. Female and male patients  $\geq 18$  years of age.
3. Subjects must have biopsy-confirmed forms of cutaneous lichen planus (CLP), mucosal lichen planus (MLP), or active lichen planopilaris (LPP) eligible for systemic therapy based on the following criteria:
  - rated IGA of  $\geq 3$  at screening and baseline (moderate or severe) **AND**
  - inadequate response to topical corticosteroids of high-ultrahigh potency in the opinion of the investigator.
4. If using any of the allowed topical treatments on the affected areas, the dose and application frequency should remain stable for 2 weeks prior to randomization and until Week 16.

### 5.2 Exclusion criteria

Subjects meeting **any** of the following criteria are not eligible for inclusion in this study.

1. Clinical history suspicious for lichenoid drug eruption.
2. Lichen planus pigmentosus.
3. Clinical picture or history suspicious of paraneoplastic mucosal lichen planus.
4. Subjects whose lichen planus is a predominantly bullous variant.
5. Mucosal LP of the oral cavity or gastrointestinal involvement requiring the patient to use parenteral nutrition or feeding tube.
6. Clinical picture of scarring alopecia **without** active inflammation.

7. Clinical picture of burnt-out cicatricial alopecia (alopecia of Brocq).
8. Patients diagnosed with frontal fibrosing alopecia (FFA) without active patches of LPP.
9. Clinical picture of LPP in patients who have already failed 3 or more systemic immunosuppressive or immunomodulatory agents (e.g. systemic steroids, hydroxychloroquine, cyclosporine, methotrexate and mycophenolate mofetil).
10. Currently enrolled in any other clinical trial involving any investigational agent or device.
11. Previous exposure to any other biologic drug directly targeting IL-17A or IL-17RA (e.g. secukinumab, ixekizumab or brodalumab) or IL-23/p19 (e.g. tildrakizumab, guselkumab, risankizumab).
12. Diagnosis of active infectious diseases of the skin, scalp or mucosa (for example bacterial, viral or fungal infections of the mouth) that may interfere with the assessment of the study disease or require treatment with prohibited medications.
13. Diagnosis of active inflammatory diseases of the skin, scalp or mucosa other than lichen planus that may interfere with the assessment of the study disease or require treatment with prohibited medications.
14. Presence of any other skin condition that may affect the evaluations of the study disease.
15. Underlying conditions (including, but not limited to metabolic, hematologic, renal, hepatic, pulmonary, neurologic, endocrine, cardiac, infectious or gastrointestinal - e.g., Inflammatory Bowel Disease) and/or presence of laboratory abnormalities which in the opinion of the investigator significantly immunocompromises the subject and/or places the subject at unacceptable risk for receiving an immunomodulatory therapy.
16. Current, severe, progressive or uncontrolled diseases that render the patient unsuitable for the trial, including any medical or psychiatric condition that, in the Investigator's opinion, would preclude the participant from adhering to the protocol or completing the study per protocol.
17. Ongoing use of ANY treatment prohibited by the protocol (for details, refer to [Table 6-2](#)).
18. Plans for administration of live vaccines during the study period or within 6 weeks before randomization.
19. Pregnant or nursing (lactating) women.
20. Women of childbearing potential, defined as all women physiologically capable of becoming pregnant, unless they are using methods of contraception during the entire study or longer if required by locally approved prescribing information (e.g. in European Union (EU) 20 weeks).  
Contraception methods include:
  - Total abstinence, when this is in line with the preferred and usual lifestyle of the patient. Periodic abstinence (e.g. calendar, ovulation, symptothermal, post-ovulation methods) and withdrawal are not acceptable methods of contraception.
  - Female sterilization (have had surgical bilateral oophorectomy [with or without hysterectomy], total hysterectomy or tubal ligation at least six weeks before taking study treatment). In case of oophorectomy alone, only when the reproductive status of the woman has been confirmed by follow-up hormone level assessment.
  - Male sterilization (at least 6 months prior to screening). The vasectomized male partner should be the sole partner for that patient.

- Barrier methods of contraception: Condom or Occlusive cap (diaphragm or cervical/vault caps).
- Use of oral (estrogen and progesterone), injected or implanted hormonal methods of contraception or other forms of hormonal contraception that have comparable efficacy (failure rate <1%), for example hormone vaginal ring or transdermal hormone contraception or placement of an intrauterine device (IUD) or intrauterine system (IUS).

In case of use of oral contraception, women should have been stable on the same pill for a minimum of 3 months before taking study treatment.

In case local regulations deviate from the contraception methods listed above, local regulations apply and will be described in the informed consent form (ICF).

Note: Women are considered post-menopausal and not of childbearing potential if they have had 12 months of natural (spontaneous) amenorrhea with an appropriate clinical profile (e.g. age appropriate, history of vasomotor symptoms) or have had surgical bilateral oophorectomy (with or without hysterectomy), total hysterectomy or tubal ligation at least six weeks prior to enrollment. In the case of oophorectomy alone, only when the reproductive status of the woman has been confirmed by follow-up hormone level assessment is she considered not of childbearing potential.

21. History of recurrent bacterial infection (at least 3 major infections resulting in hospitalization and/or requiring intravenous antibiotic treatment within the past 2 years).
22. History of congenital or acquired immunodeficiency (eg, Common Variable Immunodeficiency [CVID]).
23. Hepatitis B surface antigen (HBsAg) positive or Hepatitis B core antibody positive at screening.
24. History of Human Immunodeficiency Virus (HIV) infection.
25. Hepatitis C antibody positive at screening unless viral load is 0.
26. Evidence of tuberculosis infection as defined by a positive QuantiFERON® TB-Gold test (QFT) at screening. Patients with a positive or indeterminate QFT test may participate in the study if a full tuberculosis work-up (according to local practice/guidelines) completed within 12 weeks prior to randomization, establishes conclusively that the patient has no evidence of active or latent tuberculosis.
27. History of lymphoproliferative disease or any known malignancy or history of malignancy of any organ system treated or untreated within the past 5 years, regardless of whether there is evidence of local recurrence or metastases (except for skin Bowen's disease, or basal cell carcinoma or actinic keratosis that have been treated with no evidence of recurrence in the past 12 weeks; carcinoma in situ of the cervix or non-invasive malignant colon polyps that have been removed).
28. No additional exclusions may be applied by the investigator, in order to ensure that the study population will be representative of all eligible patients.

## 6 Treatment

### 6.1 Study treatment

The following investigational drug and comparator will be supplied and appropriately labeled by Novartis:

- **Investigational drug:** Secukinumab 300 mg, provided as 2 s.c. injections of 1 ml prefilled syringe (PFS). Each 1 ml syringe contains 150 mg secukinumab.
- **Comparator:** Placebo, provided as 2 s.c. injections of 1 ml prefilled syringe (PFS).

Each placebo pre-filled syringe contains a mixture of inactive excipients, matching the composition and the appearance of the secukinumab 150 mg dose.

#### 6.1.1 Investigational and control drugs

**Table 6-1 Investigational and control drug**

Investigational/Control Drug (Name and Strength)	Pharmaceutical Dosage Form	Route of Administration	Supply Type	Sponsor (global or local)
Secukinumab 150mg	Solution for subcutaneous injection	Subcutaneous injection	Double blind supply, 1ml pre-filled syringe	Sponsor (global)
Placebo 150mg	Solution for subcutaneous injection	Subcutaneous injection	Double blind supply, 1ml pre-filled syringe	Sponsor (global)

Secukinumab and the secukinumab matching placebo will be labeled as “AIN457 150 mg / Placebo” (1 ml) to keep the blind. Subjects will initially be instructed on how to perform the injection by site staff. They will also receive written instructions as to how to self-inject using the pre-filled syringe.

Patients or caregivers not able/willing to self-administer the drug and perform home administration, will be allowed to return to the site for administration of the medication. During those visits, no additional assessments will be performed.

#### 6.1.2 Additional study treatments

No other treatments beyond investigational drug, placebo and allowed concomitant topical treatments/background treatment are included in this trial.

#### 6.1.3 Treatment arms/group

According to their diagnosis, subjects will be assigned at Screening visit to one of the following cohorts based on the **predominant** subtype of the disease (e.g. skin lesions are clinically dominant and the primary reason for treatment: patient is assigned to the cutaneous lichen planus cohort; mucosal lesions are clinically dominant and the primary reason for treatment: patient is assigned to the mucosal lichen planus cohort):

- **Cutaneous lichen planus**

- **Mucosal lichen planus**
- **Lichen planopilaris**

Patients presenting with two concomitant subtypes of lichen planus (e.g. concomitant presence of skin and mucosal lesions) will be eligible to enter the trial provided the cohort assignment occurs following the predominant subtype.

Within each cohort patients will be randomized to one of the treatment arms in a 2:1 ratio:

- **Cutaneous lichen planus** (n=36)
  - Secukinumab 300 mg every 4 weeks (n=24)
  - Placebo for 16 weeks followed by secukinumab 300 mg every 2 weeks (n=12)
- **Mucosal lichen planus** (n=36)
  - Secukinumab 300 mg every 4 weeks (n=24)
  - Placebo for 16 weeks followed by secukinumab 300 mg every 2 weeks (n=12)
- **Lichen planopilaris** (n=36)
  - Secukinumab 300 mg every 4 weeks (n=24)
  - Placebo for 16 weeks followed by secukinumab 300 mg every 2 weeks (n=12)

Treatment is divided into 2 treatment periods:

#### **Treatment Period 1: Week 0-16**

- Patients in the active **secukinumab 300 mg every 4 weeks treatment arm** receive induction with secukinumab 300 mg s.c. at Weeks 0, 1, 2, 3, 4 and then secukinumab 300 mg s.c. every 4 weeks, meaning at Weeks 8 and 12.
- Patients in the **placebo for 16 weeks followed by secukinumab 300 mg every 2 weeks treatment arm** receive corresponding placebo injections s.c. at Weeks 0, 1, 2, 3, 4 and then every 4 weeks, meaning at Weeks 8 and 12.

#### **Treatment Period 2: Weeks 16-32**

- Patients in the active **secukinumab 300 mg every 4 weeks treatment arm** stay on secukinumab 300 mg every 4 weeks, meaning they receive secukinumab 300 mg s.c. at Weeks 16, 20, 24 and 28. In order to maintain the blinding they additionally receive placebo injections at Weeks 17, 18 and 19 as well as placebo injections at Weeks 22, 26 and 30.
- Patients from the **placebo with switch to secukinumab 300 mg every 2 weeks treatment arm** switch over to active secukinumab 300 mg every 2 weeks treatment. They receive a weekly induction with secukinumab 300 mg s.c. at Weeks 16, 17, 18, 19 and 20 and then secukinumab 300 mg every 2 weeks, meaning at Weeks 22, 24, 26, 28 and 30.

The first injection of Treatment Period 2 is given at Week 16. The last injection (secukinumab 300 mg or placebo) is given in both the treatment arms **at week 30**.

#### **6.1.4 Treatment duration**

The duration of treatment is 32 weeks, with the last injection being given at Week 30. Subjects may be discontinued earlier from treatment due to unacceptable toxicity, disease progression, or at the discretion of the investigator or the subject.

## 6.2 Other treatment(s)

### 6.2.1 Concomitant therapy

Patients entering the trial are not allowed to use any topical therapies as background treatment except the ones defined in this section. Permitted topical therapies are listed below and must be recorded in the case report form (CRF).

The medications listed below are allowed for use throughout the duration of the trial: **subjects should be on a stable dose and application frequency of topical treatments 2 weeks prior to randomization. Administration should remain stable regarding dose and application frequency during Treatment Period 1 (until Week 16)**, and it is strongly recommended to maintain it at a stable level during Treatment Period 2 (from Week 16 until Week 32).

The following topical treatments are allowed:

- **Low-moderate potency corticosteroids (Group IV, V, VI and VII as per WHO definition):**

Desoximetasone cream, 0.05%  
Fluocinolone acetonide ointment, 0.025%  
Fludroxcortide ointment, 0.05%  
Hydrocortisone valerate ointment, 0.2%  
Triamcinolone acetonide cream, 0.1%  
Betamethasone dipropionate lotion, 0.02%  
Betamethasone valerate cream, 0.1%  
Fluocinolone acetonide cream, 0.025%  
Fludroxcortide cream, 0.05%  
Hydrocortisone butyrate cream, 0.1%  
Hydrocortisone valerate cream, 0.2%  
Triamcinolone acetonide lotion, 0.1%  
Betamethasone valerate lotion, 0.05%  
Desonide cream, 0.05%  
Fluocinolone acetonide solution, 0.01%  
Dexamethasone sodium phosphate cream, 0.1%  
Hydrocortisone acetate cream, 1%  
Methylprednisolone acetate cream, 0.25%  
Triamcinolone acetonide oral rinse, 0.1%

The paste formulation of a corticosteroid is considered of comparable potency to its ointment formulation if the concentration is the same. The gel formulation of a corticosteroid is considered of comparable potency to its lotion formulation if the concentration is the same.

- **OTC emollients, shampoos and lubricants for the treatment of itch and/or pain**, e.g. anti-itch lotions containing menthol, pramoxine or antihistamines
- **(Mixed) medication for the treatment of oral pain** (e.g., lubricants, OTC mouthwashes containing diphenhydramine, viscous lidocaine, antacid, nystatin or corticosteroids **of Group IV, V, VI and VII as per WHO definition**)

Each concomitant drug must be individually assessed against all exclusion criteria/prohibited medication. If in doubt, the investigator should contact the Novartis medical monitor before randomizing a subject or allowing a new medication to be started. If the subject is already enrolled, contact Novartis to determine if the subject should continue participation in the study.

All other forms of topical treatments **for any of the 3 LP subtypes** are not allowed during the Screening and Treatment periods. All medications, procedures, and significant non-drug therapies (including physical therapy and blood transfusions) administered after the subject was enrolled in the study must be recorded on the appropriate CRFs.

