### **Follow-up:**

There is an 8-week Follow-up Period after Week 32. The End of Study is reached at Week 40. If a subject discontinues study during Follow-up period, visit Week 40 has to be performed.

**Figure 3-1** Study design

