Treatment blinding is maintained beyond the primary endpoint (week 16) throughout Treatment Period 2, which enables cross-comparison of the sequential efficacy and safety data of the 2-weekly dosing regimen in Treatment Period 2 to the 4-weekly dosing regimen in Treatment Period 1. Furthermore, it ensures that investigators remain blinded regarding the treatment subjects received during Treatment Period 1. In addition, continued blinding ensures more objective efficacy and safety assessment during Treatment Period 2.

An 8-week follow-up period will enable the assessment of disease activity [REDACTED] after the end of treatment.

The regular assessments of disease activity and clinical status ensure that safety is monitored closely and that both, subjects and investigators, have the opportunity to assess if the continued participation in the trial is to the patient's benefit. If the subject's participation is deemed not to be of benefit for the subject, she/he can exit the trial at any time.

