### 6.2.2 Prohibited medication

Use of any treatments displayed in the table below that could confound the efficacy assessment of the investigational drug is **NOT** allowed during the course of the study for **ANY** indication. All prohibited treatments should be washed out as shown in the table below. The investigator should instruct the subject to notify the study site about any new treatments. At the discretion of the investigator, if any use of a prohibited treatment presents an undue safety risk for the subject, the study treatment must be discontinued. If a live vaccination has to be administered, the study treatment must be discontinued. If a prohibited treatment is used during the study, the subject should discontinue the use of the prohibited treatment if he/she wishes to continue in the study. In case of undue safety risk for the subject, the subject should discontinue study treatment at the discretion of the investigator.

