**Table 6-2 Prohibited medication**

Medication	Washout period before randomization	Note
Ustekinumab	24 weeks	
Etanercept	4 weeks	
Biological agents targeting IL-17A or IL-17RA (e.g. ixekizumab, brodalumab)	No prior use allowed	
Biological agents targeting IL-23/p19 (e.g. guselkumab, risankizumab, tildrakizumab)	No prior use allowed	
Systemic, biological immunomodulating agents other than above (e.g. agents directed against TNF<math>\alpha</math> such as adalimumab, infliximab, certolizumab)	12 weeks	

Medication	Washout period before randomization	Note
Systemic, non-biological immunomodulating treatments (e.g. methotrexate, apremilast, systemic corticosteroids, cyclosporine, cyclophosphamide, sulphasalazine, azathioprin, mycophenolate mofetil, dapsone, hydroxychloroquine)	4 weeks	
Finasteride, dutasteride	4 weeks	
PPAR $\gamma$ agonists (e.g. pioglitazone), naltrexone, doxycycline	4 weeks	
Systemic use of griseofulvin or itraconazole	4 weeks	
Retinoids	4 weeks	
Low-level light therapy	4 weeks	
Phototherapy (e.g. UVB)	4 weeks	
Photochemotherapy (e.g. psoralen and UVA (PUVA))	4 weeks	
Topical calcineurin inhibitors (cyclosporin, tacrolimus, pimecrolimus) or topical vitamin D analogues	4 weeks	
Topical corticosteroids of high - ultrahigh potency (group I, II, III as per WHO definition)	4 weeks	If patients require topical corticosteroids, they have to be switched to the low - moderate potency corticosteroids (group IV, V, VI and VII per WHO definition) given in Section 6.2.1 . Subjects should be on a stable dose and application frequency of the low - medium potency corticosteroids 2 weeks prior to randomization. Administration should remain stable regarding dose and application frequency during Treatment Period 1 (until Week 16), and it is strongly recommended to maintain it at a stable level during Treatment Period 2 (from Week 16 until Week 32).
Topical phosphodiesterase 4 inhibitors (e.g. crisaborole)	4 weeks	
Intralesional corticosteroid injection	4 weeks	
Depot corticosteroid injection	6 weeks	

Medication	Washout period before randomization	Note
Live virus vaccinations	6 weeks	
Any investigational treatment or participation in any interventional trial	4 weeks or 5 half-lives, whichever is longer	

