### 6.2.3    Rescue medication

Use of rescue medication is not permitted in this study. Regarding the use of topical corticosteroids during the study, please see previous ([section 6.2.1](#) and [section 6.2.2](#)).

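### For topical lichen planus treatments, Protocol 6.2.1 implies that the ban stops at Week 32 while 6.2.2 carries it to Week 40, so the Week 36 and 40 efficacy summaries may be confounded

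*Protocol*

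**What the plan says.** Protocol section 3 divides the study into four periods: Screening, Treatment Period 1, Treatment Period 2 (ending at Week 32) and an 8-week Follow-up. It adds: "The End of Study is reached at Week 40".

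Four statements then bear on topical treatment.

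- Section 6.2.1 opens without an end date: "Patients entering the trial are not allowed to use any topical therapies as background treatment except the ones defined in this section". Later in the same section, all other topical treatments for any of the three subtypes "are not allowed during the Screening and Treatment periods". Follow-up is not named.
- Section 6.2.2 says that the treatments in Table 6-2 are not "allowed during the course of the study for" any indication. The table includes high to ultrahigh potency topical corticosteroids, topical PDE4 inhibitors and "Topical calcineurin inhibitors (cyclosporin, tacrolimus, pimecrolimus) or topical vitamin D analogues".
- Section 6.2.3: "Use of rescue medication is not permitted in this study".
- For the permitted topicals, 6.2.1 requires a stable dose and frequency to Week 16, and after that "it is strongly recommended to maintain it at a stable level during Treatment Period 2", that is, to Week 32. It says nothing about stability in Follow-up.

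On the purpose of Follow-up, section 4.1 says: "An 8-week follow-up period will enable the assessment of disease activity" after treatment ends (part of that sentence is blacked out). Table 8-1 schedules IGA and the other efficacy scales in Follow-up, and SAP 2.6.1 summarises them by visit to the end of study. SAP 2.6.3 substitutes the baseline value after treatment discontinuation by Week 32. Its only other rule is that missing values unrelated to discontinuation are analysed as observed.

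**The concern.** The same drugs, such as a potent topical steroid or topical tacrolimus, fall under two statements with different time limits. A site that works from 6.2.1 can conclude that the restriction has lapsed once the patient passes Week 32. A site that works from 6.2.2 will hold it to Week 40.

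Follow-up is where the trial observes completers off drug. Suppose a patient relapses at Week 34. If a potent topical is restarted, that patient may be graded clear or minimal at Week 40 and be read as having kept the benefit of secukinumab. If it is not restarted, the relapse shows. If sites differ, the Week 36 and 40 summaries mix the two situations, and the planned tables would not reveal the mix. Two patients in the same state could also be managed differently because their sites relied on different sections.

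**Working it through.** No plan figure attaches to this point. The plan's own design figure, a 71% chance of a positive result per cohort (24 versus 12 patients, 50% versus 20% response), reproduces as 0.712 by exact enumeration. It concerns Week 16 and does not move.

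**1. The time limits side by side, for a patient who completes both treatment periods**

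| Text | Treatments covered | Stated period | Follow-up, Weeks 32 to 40 |
|---|---|---|---|
| 6.2.1, opening | unlisted topicals as background | none given | not addressed |
| 6.2.1, later sentence | all other topicals for lichen planus | Screening and Treatment | left out |
| 6.2.2 with Table 6-2 | listed topicals; systemic, light and intralesional treatments | whole study | barred |
| 6.2.3 | rescue medication | whole study | barred |
| 6.2.1, stability of permitted topicals | permitted list | required to Week 16, advised to Week 32 | not addressed |

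The later sentence in 6.2.1 and section 6.2.2 overlap on the Table 6-2 topicals, and only there do two time limits meet. Elsewhere 6.2.1 uses whole-trial wording when it says how long the permitted topicals may be used, so the narrower wording can fairly be read as deliberate. Systemic, light and intralesional treatments appear only in 6.2.2 and have one scope.

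**2. Would the drug use be visible?**

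- Last injection: Week 30, Day 211. Week 40 visit: Day 281 (Table 8-1).
- SAP 2.4.4 counts as concomitant any medication taken up to 84 days after the last dose: 211 + 84 = Day 295, after Day 281.
- Counting from the last active dose in the Q4W arm (Week 28, Day 197) gives 197 + 84 = Day 281, the Week 40 day itself.

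Use in Follow-up is therefore recorded and inside the window. But SAP 2.4.4 tabulates it by Treatment Period 1 and entire treatment period, so starts after Week 32 are not shown separately.

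**3. Which endpoints are exposed?**

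Week 36 falls 6 weeks after the last active dose in the Q2W arm ((253 − 211)/7) and 8 weeks after it in the Q4W arm ((253 − 197)/7). Week 40 falls 10 and 12 weeks after. A topical started after Week 32 cannot affect Week 16 or Week 32.

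**4. Size per patient**

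Planned arms per cohort are 24 (Q4W) and 12 (placebo then Q2W). The change in response rate is k divided by the arm size. The documents give no value for k, the number of patients whose response status depends on a restarted topical, so the counts below are assumptions.

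| k (assumed) | of 24 | of 12 |
|---|---|---|
| 1 | 4.2 points | 8.3 points |
| 2 | 8.3 points | 16.7 points |
| 3 | 12.5 points | 25.0 points |

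The 12 is a planned maximum for Q2W: placebo patients with IGA 0 or 1 at Week 16 do not switch, and drop-outs are not replaced. With fewer patients, each counts for more.

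**The case against.** The strongest reply is that both sections can be obeyed at once. Section 6.2.1 grants no permission for Follow-up; it is silent. Section 6.2.2 is an express prohibition, and 6.2.1 itself tells the site to check each concomitant drug against the prohibited list and to ask the medical monitor when in doubt. This stands: the conflict is by implication, and uneven practice between sites is the likely result.

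Second, the data are descriptive. The decision criteria apply at Week 16, there is no concurrent placebo after that, and SAP Table 2-1 names Follow-up only for disposition. This also stands and limits the weight of the point, although SAP 2.6.1 does carry the efficacy summaries to study end.

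Third, blacked-out text might hold a rule. SAP 5.4.1.2 lists prohibited medication and changes in permitted topicals as intercurrent events, and how they are handled is not readable. That section is stated to concern the primary endpoint, so a rule for Weeks 36 and 40 there is unlikely, but it cannot be excluded there or in other redacted parts.

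Fourth, patients enter after an inadequate response to potent topical steroids, so one should not assume that restarting them would restore response in many. This is fair. Other topical classes in Table 6-2 could differ, and the documents settle neither question.

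**Conclusion.** The time limits for topicals differ between 6.2.1 and 6.2.2 and need reconciling. Until they are, the as-observed Week 36 and 40 summaries may be confounded by restarted potent topicals. The lack of any stability request for permitted topicals after Week 32 adds to this even where every site follows 6.2.2. The size is unknown: about 4.2 or 8.3 points per affected patient at the planned arm sizes, with the number of such patients an assumption.

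A reader might infer more, and the documents do not support it:

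- *That the ban on lichen planus treatment in general ends at Week 32.* The sentence in 6.2.1 covers topicals only.
- *That either every patient or no patient may restart a potent topical.* The first reading takes permission from silence and sets aside an express prohibition.
- *That the Follow-up results cannot be interpreted.* Use is recorded and falls inside the SAP's concomitant-medication window, so affected visits can be identified.
- *That a particular bias in the response rate can be stated.* No document gives a restart rate or a response rate after restart.

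The Week 16 primary endpoint and the Week 32 endpoints are unaffected.

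**What to change.** **Protocol.** Reconcile 6.2.1, 6.2.2 and 6.2.3 so that one period is stated for topical treatments in Follow-up. Which period is a clinical decision for the sponsor. One sentence should be enough.

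**SAP, Weeks 36 and 40 only.**

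- Show, by cohort and arm, how many patients started a Table 6-2 treatment after Week 32.
- Report IGA 0/1 and the response of at least 2 points with those patients counted as non-responders, beside the as-observed rate.
- Describe changes in permitted topicals separately and do not count them as non-response. A patient may reduce or stop a topical because the disease has improved, and the protocol sets no stability rule after Week 32.

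**Cost.** A few table rows. Concomitant medication is already collected in Follow-up, so no new data are needed. The stated Follow-up response rate may come out lower in the added rows.
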